1. INTRODUCTION

This Phase I / II study will examine the safety, tolerability and immunogenicity of the GLS-5310 DNA vaccine against the Severe Acute Respiratory Syndrome coronavirus, type 2 (SARS-CoV-2) when administered intradermally (ID) with the JM-11 device to healthy individuals without a history of documented SARS-CoV-2 infection.

1.1 Background and Rationale

SARS-CoV-2 is the third highly pathogenic coronavirus identified to cause disease in humans since 2002. SARS-CoV caused a total of approximately 10,000 cases worldwide between 2002 and 2003 with a global mortality rate of 10%. The Middle East respiratory syndrome coronavirus (MERS-CoV) was first identified in 2012 and has resulted in fewer than 3,000 cases worldwide but with a mortality rate of 36%.

SARS-CoV-2 emerged in the last months of 2019. as of October 2020 Global case rates have exceeded 40 million with greater than 1 million deaths. Many countries are currently experiencing a 2nd wave of infection with increasing case rates, hospitalizations, and death rates.

Currently, greater than 200 vaccine candidates against SARS-CoV-2 have been developed with a number advanced to clinical trials ¹. Approximately 10 vaccines have been granted emergency use authorization in multiple countries. The vast majority of vaccine candidates specifically target the coronavirus spike (S) protein ^{2,3}, while others are versions of inactivated viruses and target the entire virus ⁴.

1.1.1 The SARS-CoV-2 Spike protein as a vaccine target

The coronavirus S protein has been the dominant antigenic target for SARS-CoV, MERS-CoV, and SARS-CoV-2 vaccine design. Our MERS-CoV DNA vaccine, GLS-5300, also targets the S protein and has been shown to induce strong antibody and T cell responses in healthy adults ^{5,6}. Similarly, most of the SARS-CoV-2 vaccine candidates in pre-clinical and clinical development have targeted the coronavirus S protein as a single antigen.

Previous studies of SARS-CoV vaccine constructs in pre-clinical studies, summarized in the GLS-5310 Investigator's Brochure (IB), showed that S-only vaccines were in general not able to induce sterilizing immunity in animal models of infection. A similar phenomenon was seen for MERS-CoV vaccines. SARS-CoV-2 vaccines in development have also shown variable ability to induce sterilizing immunity. Rhesus macaques inoculated with the ChAdOx1 vaccine encoding the SARS-CoV-2 S protein developed less clinical disease, however, an equal number of animals in the vaccine and control groups demonstrated high pulmonary viral load levels ². In this same study, nasal RNA viral loads did not differ between vaccinated and control animals. A separate research group evaluated a series of S protein DNA vaccines ⁷. While these vaccine constructs induced high levels of neutralizing antibodies and T cell responses in Rhesus macaques, bronchoalveolar lavage (BAL) samples showed continued viral presence and thus demonstrated that non-sterilizing immunity was obtained in 50-75% of animals ⁷. Nasal swabs from vaccinated animals evaluated for the presence of virus showed no difference from control animals. Antibodies from vaccinated animals induced antibody dependent neutrophil or NK, or monocyte phagocytosis. However, whether this phenomenon correlated with greater viral survival and/or correlated with any clinical signs was not reported ⁷. Finally, an inactivated SARS-CoV-2 vaccine induced high levels of binding and neutralizing antibodies in rats and macaques ⁴. Macaques demonstrated

dose-dependent protection such that animals receiving 3 µg of vaccine had low levels of virus in the lung, whereas those inoculated with 6 µg had no detectable virus in the lung, however, virus was present in throat swabs regardless of high and low-dose ⁴. Importantly, vaccinated animals still developed moderate pulmonary inflammation on histology ⁴.

The coronavirus nucleocapsid (N) protein is also very immunogenic with high levels of antibody and T cell responses seen among patients recovered from infection. Moreover, cellular responses against the SARS-CoV N have been found to be persistent over years. However, inclusion of N as a vaccine antigen may be contraindicated as SARS-CoV vaccines that included this protein induced significant immune priming resulting in an intense eosinophilic pneumonitis whereas the viral S did not ^{8,9}. A commentary by Hotez *et al.* cited the N as the inciting antigenic target inducing a Th17 immune response leading to immune priming ¹⁰. Consensus recommendations of the Coalition for Epidemic Preparedness and Innovation (CEPI) and the World Health Organization (WHO) similarly recommend avoidance of the SARS-CoV-2 N in vaccine constructs ¹¹.

To summarize, while the SARS-CoV-2 S protein is an appealing target, it may not induce sterilizing immunity when used as a sole vaccine antigen and inclusion of the coronavirus N protein may be contraindicated in a vaccine. In the next section we discuss our rationale and the merits of including ORF3a as a second vaccine antigen.

1.1.2 The SARS-CoV-2 ORF3a protein as a vaccine antigenic target

Studies of patients recovered from SARS-CoV infection have shown good correlation between the presence of binding and neutralizing antibodies ¹². Antibodies against the SARS-CoV S protein were relatively short-lived with a half-life of about 6 weeks and a decay more rapid in those with more severe disease ¹². In contrast, T cell responses were persistent and long-lived to at least 4 years with the greatest magnitude of responses against the replicase, S, ORF3a, ORF7, and NP ¹³. T cell responses against the S, ORF3, membrane (M), and S were the most prevalent among convalescent patients. A DNA vaccine against the SARS-CoV ORF3a was shown to be safe and able to induce high levels of humoral and cellular immune responses in mice ¹⁴.

For SARS-CoV-2, both S and ORF3a have similarly been shown to be potent inducers of T cell responses in recovered patients ¹⁵, and its inclusion in our vaccine is primarily as a second immunogen to strengthen the overall T cell response. Importantly, T cell responses against S and ORF3a were the most prevalent among patients recovered from natural SARS-CoV-2 infection and reactivity was observed among the HLA-restricted epitopes that are most prevalent in the US and Korean populations ¹⁶.

In addition to the lack of sterilizing immunity induced by S protein vaccines, a number of recent reports raise additional potential concerns as to the reliance on vaccines that only target the S protein. A novel S mutation, D614G, that has been identified among persons infected with SARS-CoV-2 enhances viral infectivity and is associated with the loss of neutralizing activity in approximately 7% of such individuals ¹⁷. Second, the SARS-CoV-2 S protein has been shown to undergo conformational changes within the acidic environment of endosomes, which abolishes the effects of bound neutralizing antibodies ¹⁸ – thus raising the concern that neutralizing antibodies may be ineffective or less effective than predicted by *in vitro* assays.

Finally, antibodies against SARS-CoV-2 decline quickly after infection, often becoming undetectable in as short as 90 days post-infection ¹⁹, suggesting the need for T cell immunogenicity for a long-lasting effect. Two recent studies provide critical evidence that ORF3a is a major immunogen of SARS-CoV-2 within the immediate period post-infection ^{15,16}. T cell

[figure not shown]
responses against ORF3a were present in 80-100% of sampled convalescent individuals¹⁶. Perhaps even more critical is that only S and ORF3a contained HLA A*02:01 and A*24:02 restricted epitopes, highly prevalent HLA haplotypes in the US and Korea²⁰.

The GLS-5310 vaccine was designed to target the S and ORF3a viral antigens of SARS-CoV-2 to generate robust immune responses from both B and T cells that may work synergistically to increase vaccine effectiveness. Pre-clinical studies of GLS-5310 are detailed in the IB. Pre-clinically, we have shown that each antigen is independently expressed from our DNA plasmid vaccine construct *in vitro*, and together are immunogenic *in vivo* with each inducing strong B and T cell immune responses, including high levels of binding and neutralizing antibodies, following intradermal administration of GLS-5310 with the JM-11device. Moreover, pre-clinical data has demonstrated immune responses equal to or greater than those elicited with use of electroporation.

1.2 Investigational Agent

GLS-5310 DNA plasmid vaccine contains a single plasmid, pGO-1002 (Figure 1.2-1), formulated at 6 mg/ml in 1X saline sodium citrate (SSC) buffer.

Figure 1.2-1: pGO-1002 plasmid

1.3 Dose and Regimen Rationale

For this Phase I / II study, GLS-5310 will be given at one of two dose levels (0.6 mg and 1.2 mg) administered intradermally (ID) by injection followed by suction using the JM-11device. Vaccine will be administered at baseline and again at either 8 or 12 weeks.

First of all, the factors to consider for setting the capacity are as follows.

The DNA vaccine is not directly vaccinated with a viral antigen that induces a vaccine immune response, but if it is vaccinated in the form of DNA, which is a gene encoding the antigen, it is delivered into cells, and then the antigen is produced and secreted from the DNA through transcription and translation processes. Therefore, the immune response of the vaccine does not increase directly in proportion to the administered dose. Therefore, rather than setting the clinical dose through animal experiments like the existing vaccine, the standard dose is set in consideration of the administration route based on the final concentration of the manufactured

DNA vaccine, and the optimal dose is increased or decreased through clinical trial. It is common to find. For example, the maximum concentration of our DNA vaccine is 6-10mg/mL, and in general, the intramuscular vaccination volume is 1mL and the intradermal vaccination volume is 0.1mL. Applying this, the standard dose for clinical trials is 6-10 mg dose for intramuscular vaccination, and 0.6 to 1.0 mg dose for intradermal vaccination.

The dose levels chosen are consistent with the dosage range for our prior MERS-CoV DNA plasmid vaccine, GLS-5300, studies, and the above contents. In the Phase I study of GLS-5300, vaccine was administered IM at doses of either 0.6, 2, or 6 mg (NCT02670127⁵) and in the Phase Ib/Ila study GLS-5300 was administered ID at doses of either 0.3 or 0.6 mg (NCT03721718⁶). Results of these two studies demonstrated no clear dose effect for the GLS-5300 vaccine given over a 10-fold range from 0.6 mg to 6 mg. In addition, as a result of pre-clinical efficacy evaluation of GLS-5310, the level of vaccine immune response induced by the use of an electroporator and a suction was similar. Therefore, although the clinical study of the MERS DNA vaccine used electroporation, it can be used as the basis for the dose setting of the GLS-5310 clinical study. Therefore, when the maximum concentration of the drug product of GLS-5310 is 6mg/mL and 0.1mL, which is the volume for intradermal vaccination, is applied, the standard dose becomes 0.6mg. The second dose was set to a 1.2mg dose, which was doubled from the 0.6mg dose, using the results of the clinical study of the MERS DNA vaccine, and the optimal dose will be selected through a phase 1 study of this clinical trial protocol.

To select the vaccination interval of GLS-5310, an interim analysis of the phase 1/2a clinical study of the MERS DNA vaccine (GLS-5300) was performed. The immune responses in the 3 times vaccination group (0-4-12 weeks) and the 2 times vaccination group (0-8 weeks) were compared. The binding antibody titers and neutralizing antibody titers at the time point of 8 weeks (after the second dose and after the first dose, respectively) of the 3 times vaccination group and the 2 times vaccination group were similar. At 12 weeks (all after the second dose), the 2 times vaccination group was rather higher.

As a result, in the case of DNA vaccine, it was confirmed that setting the interval between single vaccination and 2 times vaccination of 8 weeks or more could induce a more effective vaccine immune response, and this was applied to GLS-5310 vaccine.

1.3.1 Function of Suction after intradermal administration of DNA vaccine

For the purpose of researching gene therapy products, when a plasmid, a naked DNA encoded with a target gene, was administered in the body and then suction, the result of protein expression from the target gene at that injection site has been studied and published several times. At this time, the plasmid itself can be delivered intracellularly when administered into the human body, but when suction is applied, it can be seen that it induces physical stimulation at the injection site of administration and affects gene expression in the plasmid. The suction device is an industrial product device for beauty or an equivalent or higher device that simply applies suction pressure.

The main component of DNA vaccines is a plasmid containing a gene encoding an antigen of a virus that causes disease. When the DNA vaccine is administered intradermally, the vaccine

immune response is induced by antigens generated from the DNA vaccine. At this time, when the inhalation pressure used in the gene therapy research is applied, it provides a physical stimulation to the intradermal cells at the injection site, thereby giving a secondary effect of enhancing the vaccine immune response.

1.4 Risk/Benefit Assessment

In accordance with the International Conference on Harmonization (ICH), this study has been designed to minimize the risk to study participants.

This study of GLS-5310 vaccine is designed to determine whether the vaccine can induce immune responses in an effort to prevent disease from SARS-CoV-2. The adverse effects of GLS-5310 vaccine are unknown, however, GLS-5310 is similar to other GeneOne Life Science vaccines. These include Phase I and Phase Ib/Ila studies of GLS-5300 DNA vaccine against MERS-CoV. Results of the Phase I study of GLS-5300 have been published ⁵ with no vaccine associated serious adverse events (SAEs) and most common adverse events (AEs) were related to electroporation-based administration. Preliminary results of the GLS-5300 Phase Ib/Ila study were presented at the May 2020 meeting of the American Society for Gene and Cell Therapy ⁶ with no vaccine associated SAEs. Treatment assignment will be unblinded at visit 4 and participants and site personnel informed of vaccine or placebo status. Subjects that had been assigned to placebo will be offered vaccination with GLS-5310 clinical trial drugs. However, the information on safety and efficacy may be limited if an approved or an emergency use authorized vaccine is administered after vaccination of the clinical trial study drug.

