3. STUDY DESIGN

This Phase I / II study will assess the safety, tolerability, and immunogenicity of GLS-5310 DNA vaccine.

The Phase I study is an open-label, dose escalation study to assess two dose levels of GLS-5310 DNA vaccine (0.6 and 1.2 mg) and given via two vaccination regimen (0-8 weeks and 0-12 weeks). Participants will be randomized to one of the three treatment arms. GLS-5310 will be administered via intradermal (ID) injection using the Mantoux technique followed by suction applied over the vaccination site using the JM-11 device. The primary outcome measures are the safety and tolerability of GLS-5310 given ID with JM-11 and binding antibody responses elicited by vaccination. Secondary outcome measures are the T cell responses elicited to vaccine antigens and neutralizing antibody titers.

Dose escalation within the Phase I portion of the study will occur as follows. Study arm 1a (0.6 mg per vaccination) will be vaccinated and followed to the Week 1 safety visit. If no vaccine-associated severe adverse events (SAEs) have been documented, then enrollment into study arms 1b and 1c (1.2 mg per vaccination) will occur in a randomized manner. An interim analysis will occur after visit 4, four weeks after the 2nd vaccination to assess safety and binding antibody responses. Escalation to Phase II will occur based on this analysis. The choice of regimen for the Phase II study will be determined after review of study objectives.

The Phase IIa study is designed as a randomized, double-blind, placebo-controlled study with only a single active study drug arm. Subjects will be randomized to receive either placebo or GLS-5310 vaccine in a 1:2 ratio. The primary and secondary goals of the Phase II study are the same as the Phase I study. An interim analysis will be performed at Visit 4, one month after the final vaccination. The study will be unblinded at the post-vaccination visit (study visit 4) at which time subjects will be informed of their treatment assignment. Subjects who were assigned to the placebo group will be offered to be vaccinated with GLS-5310. Subjects assigned to the placebo group who choose to be vaccinated with GLS-5310 will be followed for a year from 1st GLS-5310 vaccination (Table S4); subjects assigned to the placebo group but who decline vaccination with GLS-5310 will be followed for a year from study entry as per the original study protocol.

[Sub-studies]

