The test will assess cellular and humoral immune responses in blood samples collected after baseline and vaccination according to Table S2.

The duration of this clinical trial is as follows.

About 20 months from the date of approval of the clinical study by the Ministry of Food and Drug Safety and the Institutional Review Board

- Recruitment period for test subjects: about 5 months
- Clinical trial period for each subject: at least 48 weeks

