7.1.5 Visit 4: Post-vaccination follow-up, unblinding

Study procedures to be completed include:

- Review and record concomitant medications
- Perform targeted physical exam (relevant to participant system-specific complaints)
- Perform and record vital signs
- Review and record adverse events
- Review and record injection site reactions
- Collect blood for hematology and chemistry
- Collect blood for immunology testing (serum and PBMCs)
- Inform participant of their treatment assignment
 - For those who received placebo, ask whether they would like to start vaccination series with GLS-5310(Refer to Section 7.2)

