8.1.5 Safety Laboratory Evaluations

Blood for a complete blood count with differential(RBC, hemoglobin, hematocrit, platelet, WBC, neutrophil, lymphocyte, monocyte, eosinophil, basophil) and chemistries (consisting of sodium, potassium, blood urea nitrogen (BUN), creatinine, glucose, ALT, and bilirubin, Ca, Cl, AST, ALP, CPK, albumin, total protein, total cholesterol) will be performed at Visits 1, 2, 4 and 8. A urine pregnancy test will be performed at Visit 1 and Visit 3 for those of childbearing potential. Laboratory test abnormalities are generally not recorded as adverse events or serious adverse

events. According to the judgment of the investigator, a clinically significant abnormal value is reported as an adverse event, and if it is related to a clinical adverse event, it is reported as the name of the adverse event. For laboratory test results, normal/abnormal evaluation is performed according to the normal range of the clinical trial site, and the severity is evaluated by the Toxicity Grading Scale.

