8.3.3 Unblinding

The Phase IIa portion of the study will be unblinded at study visit 4 and subjects informed of their treatment status. Subjects assigned to the placebo group may elect to receive vaccine. Regardless of later vaccination status, all subjects will remain in study for safety evaluations.

In the Phase IIa study, all subjects, including those who were assigned to a placebo control group after unblinding, but subjects assigned to placebo who chose not to receive GLS-5310, will be followed for a year from study entry.

Treatment assignments through to the post-vaccination visit (Visit #4) should be maintained as blinded unless unblinding is considered critical to the care and well-being of the subject and that knowledge of the treatment assignment will affect medical management and medical decision making. Unblinding prior to visit #4 should occur following discussion with Sponsor Medical Monitor. However, emergency unblinding can occur if the Investigator deems that such a delay would unduly harm the subject and that knowledge of the treatment assignment is a critical factor in medical decision making versus discontinuation or temporary discontinuation of a study drug until discussion with the Medical Monitor. In the case of unblinding, the Investigator is not required to inform the Sponsor of treatment assignment. Unblinded treatment assignment should be made known only to those who require such information as part of medical decision making and for those involved in Safety reporting to Health Authorities and/or the relevant IRB or local oversight body. In addition, the immunogenicity assay staff must remain blinded until the assay is complete.

Treatment assignments for immunologic measurement should be maintained as feasible throughout the study.

The Investigational Pharmacy at each site will maintain a listing of treatment assignments and will provide a mechanism for unblinding in emergency situations.

After unblinding, collect safety and efficacy results as much as possible even if you are not in the GLS-5310 vaccination group.

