11.1 Data Sets to be Analyzed

- The intention to treat population (ITT) includes all participants who sign informed consent.
- The modified intention to treat population (mITT) includes all participants who sign informed consent and who has received at least one administration of study drug. The mITT population will be the primary analysis population for outcomes.
- The safety set (SS) includes all participants who have received at least one dose of study medication. The SS will be the primary group for safety evaluations and outcome. Analysis of immune responses will be performed only for available samples.

Per-protocol (PP) analysis set includes all participants who complete the trial and who receive all vaccinations and have no significant protocol violations. Participants in this sample will be grouped to treatment arms they actually received. This set will be used as a sensitivity analysis to summarize the primary and secondary efficacy outcomes. For secondary and exploratory assessments of antibody and T cell immune responses, denominators will include only those participants who are SARS-CoV-2 seronegative at baseline. Unevaluable samples will not be considered as part of the denominator at relevant time points. For study participants who are seropositive at baseline, separate assessment of antibody and T cell responses will be performed.

The Phase IIa portion of the study will be unblinded at the post-vaccination visit (visit 4) and all persons who were randomized to the placebo arm offered vaccination with GLS-5310. Safety assessments will be determined based on the actual treatment received. Persons randomized to the placebo group who elect vaccination with GLS-5310 will then be considered to cross-over to the vaccination group as of Week 12. Persons randomized to the placebo group, and who decline vaccination will remain as part of the placebo group, regardless of whether such persons receive any other COVID-19 vaccine. Any study participant who receives an approved COVID-19 vaccine will remain as part of the group assignment as above.

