4.1 Interim Analysis

Interim analyses were performed in stages.

- **Stage 1:** An assessment of AE's was performed after study Visit 1 for Group 1a.
- **Stage 2:** When all Phase I subjects (Groups 1a, 1b and 1c) had completed Visit 4, an interim analysis was performed to evaluate safety and antibody response.
In order for the study to move into Phase IIa study, the seroconversion rate for the binding antibody responses must be >70%. In addition, the incidence of Serious Adverse Events (Grade 3 or higher) related to the investigational product should be no more than 1 case.
- **Stage 3:** An interim analysis of Phase IIa study was performed after all patients complete their Visit 4. The purpose of this interim analysis was to provide options to placebo vaccinated subjects and to assess the safety of the vaccine after the second dose. For the interim analysis of Phase IIa, database locking was implemented before unblinding.

The study is unblinded at the post-vaccination visit (study Visit 4) at which time subjects are informed of their treatment assignment. Subjects who were assigned to the placebo group are offered to be vaccinated with GLS-5310. Subjects assigned to the placebo group who choose to be vaccinated with GLS-5310 are followed for a year from 1st GLS-5310 vaccination; subjects assigned to the placebo group but who decline vaccination with GLS-

CONFIDENTIAL

5310 are followed for a year from study entry as per the original study protocol.

5. Determination of Sample Size

This is an exploratory and descriptive Phase I/Ila clinical trial to evaluate the safety and immunogenicity of GLS-5310 for the purpose of preventing COVID-19, and dose not test statistical hypotheses, so the sample size is set within the limit of satisfying the research purpose. In the Phase I clinical trial, 45 subjects who meet the inclusion and exclusion criteria are registered to secure 15 subjects based on the allocation of each vaccination group. In the Phase Ila clinical trial, it is planned to secure 120 subjects based on randomization.

Randomization is performed 1:1 in 1b and 1c groups of Phase I clinical trial according to the planned random number, and 1:2 in placebo and vaccination groups in Phase Ila clinical trial to determine the difference between placebo and vaccination groups.

6. Analysis Sets

Safety and tolerability analyses will be performed on Safety Set.

✓ **Intention to treat (ITT)**

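### The documents disagree on whether Phase IIa is unblinded at each participant's own Visit 4 or after database lock; under the visit-level text, nothing requires the dose-2 safety judgements to be recorded before the code is disclosed.

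*Protocol*

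**What the plan says.** **Unblinding at the participant's own visit.** Protocol 1.4: "Treatment assignment will be unblinded at visit 4 and participants and site personnel informed of vaccine or placebo status". Protocol 3 (and the synopsis in the same terms): "The study will be unblinded at the post-vaccination visit (study visit 4) at which time subjects will be informed of their treatment assignment". The Visit 4 procedure list in 7.1.5 ends with "Inform participant of their treatment assignment", after AE review, injection-site review and the safety bloods. Protocol 8.3.3 protects the blind only up to that visit: "Treatment assignments through to the post-vaccination visit (Visit #4) should be maintained as blinded". Under 11.1, placebo participants who accept the vaccine "will then be considered to cross-over to the vaccination group as of Week 12". The title of Table S4 has them choosing at Visit 4, and the synopsis gives them 60 weeks of follow-up in total.

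**Unblinding after lock.** The synopsis (safety evaluation analysis method) and protocol 11.8 say Phase IIa is unblinded for analysis after database lock. SAP 4.1 Stage 3 places the interim after all participants' Visit 4, gives offering options to placebo participants as one of its purposes, and adds: "For the interim analysis of Phase IIa, database locking was implemented before unblinding". The paragraph that follows repeats that the study is unblinded at Visit 4, when participants are told.

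**Who judges safety.** Protocol 8.1.5 schedules hematology and chemistry at Visits 1, 2, 4 and 8 and says: "According to the judgment of the investigator, a clinically significant abnormal value is reported as an adverse event". Causality is the investigator's decision (8.1.2.1.7). Diary entries are evaluated by the investigator for clinical significance (7.3.3), and Table S2 places collection and review of the dose-2 diary at Visit 4.

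**The concern.** Safety is a primary endpoint, and the vaccine-placebo comparison up to Visit 4 is the only one made before placebo participants can cross over. Protocol 11.3.1 bases the main safety summary on events within 28 days of administration; for dose 2 that period ends, nominally, at Visit 4.

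If the code is disclosed at the visit where blood is drawn, and results are read afterwards, an investigator who knows the allocation decides whether an abnormal value is clinically significant, whether it becomes an AE, and whether it is related. Those decisions feed the Normal/NCS versus CS shift tables (SAP 10.4) and the AE and ADR tables (SAP 10.2), which would be reported as part of a double-blind comparison. Protocol 8.3.3 keeps assay staff blinded until the assay is complete; safety assessors have no equivalent protection.

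**Working it through.** **1. Which timing does the protocol's own figure imply?** Visit 4 is at Week 12 (Table S2) and Table S4 runs to Week 48. 12 + 48 = 60 weeks, which reproduces the synopsis total. It holds only if each placebo participant is unblinded, and starts the vaccine, at their own Week 12.

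**2. What does lock-first imply?** Let Phase IIa accrue over R weeks. The last Visit 4 is then at Week R + 12 on the first participant's clock, and that participant's total follow-up is at least (R + 12) + 48 = R + 60 weeks, plus time to lock. That gives 64 weeks for R = 4, 72 for R = 12 and 81.7 for R = 21.7. The 60 weeks and the Week 12 cross-over both fail, so the two timings cannot both describe disclosure to participants.

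**3. Which laboratory sets follow dose 2?** Dose 2 is at Week 8. Of the visits in 8.1.5, two come later: Visit 4 (12 − 8 = 4 weeks after) and Visit 8 (48 − 8 = 40 weeks after). Visit 8 comes after unblinding and any cross-over, so Visit 4 is the only set that precedes both. Section 7.1.3 also lists safety bloods at Visit 3, unlike 8.1.5 and Table S2, but before the injection in its list, so this does not change the result.

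**4. What is exposed under the visit-level text?**

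| Item | Exposed? | Basis |
|---|---|---|
| CS/NCS call on Visit 4 values | Yes, unless results are already back | 8.1.5, SAP 10.4 |
| Causality of laboratory AEs | Yes, on the same condition | 8.1.2.1.7 |
| Clinical significance of dose-2 diary entries | Yes, unless reviewed first; 7.1.5 has no diary step | Table S2, 7.3.3 |
| Numeric change; Low/Normal/High shift | Largely not | SAP 10.4 |
| Toxicity grade | Largely not; fixed scale | 8.1.2.1.6, 8.1.5 |
| AE and injection-site review at the visit | Listed before disclosure | 7.1.5 |
| Antibody and T-cell assays | No; assay staff blinded | 8.3.3 |

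**5. Disclosure across participants (secondary).** Assume uniform accrual of 120 participants over R weeks, with the first disclosure at Week 12. The share receiving dose 2 after it is max(0, (R − 4)/R); for dose 1 it is max(0, (R − 12)/R). Protocol 3 gives "Recruitment period for test subjects: about 5 months" without splitting it by phase; 5 months is about 21.7 weeks.

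| R (weeks) | Dose 2 after first disclosure | Dose 1 after first disclosure |
|---|---|---|
| 4 or less | 0% | 0% |
| 8 | 50% (60) | 0% |
| 12 | 67% (80) | 0% |
| 16 | 75% (90) | 25% (30) |
| 21.7 | 82% (98) | 45% (54) |

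The last row assigns all recruitment time to Phase IIa. The clock starts at the first disclosure anywhere in the trial; with five sites, staggered starts would lower the share whose own site already knew an allocation.

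**The case against.** The strongest reply is that the SAP describes lock-first. Stage 3, in the past tense, puts the interim after everyone's Visit 4, ties it to the placebo offer and says lock preceded unblinding; the protocol says twice that unblinding for analysis follows lock. If that order governed disclosure to sites and participants, every Visit 4 judgement could have been complete first. This is a fair reading, and it is why the point is framed as a contradiction. It does not close the matter: the protocol sentences speak of unblinding for analysis, the SAP sentence is tied to the interim analysis, and SAP 4.1 then repeats disclosure at Visit 4.

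It is also fair that no laboratory turnaround is given, so late results are an assumption; that most laboratory summaries need no investigator judgement; and that the SAP calls the trial exploratory and descriptive. These limit the size of the problem without supplying the missing order of steps.

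A reader might infer that Visit 4 holds the only laboratory results after dose 2. It does not; Visit 8 has them too. A reader might also infer that disclosing early allocations unblinds later participants. The documents do not show this: syringes carry only the subject ID (6.2), placebo is the same buffer at the same vial volume (6.1), each participant has an assigned suction device (6.10), and no placebo rate of injection-site lesions is given. Visible lesions are listed as common (8.1.2.1.3), so pattern recognition by staff is possible but not demonstrated.

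**Conclusion.** The point stands as an unresolved contradiction with a specific consequence. If the visit-level text governs, the CS/NCS and causality decisions on the only laboratory set between dose 2 and unblinding, and the clinical evaluation of the dose-2 diary, can be made with the allocation known, because no passage requires them to be recorded first. This rests on results or diary review coming after disclosure, which the documents neither state nor exclude. If lock-first governed disclosure to sites and participants, the consequence falls away, but the 60-week total and the Week 12 cross-over are then wrong.

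The documents do not support saying that these assessments were in fact made unblinded. Nor do they support treating rolling disclosure as an established bias: its reach runs from 0% to 82% of participants for dose 2, depending on an accrual time that is not given, and its mechanism is unproven.

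**What to change.** 1. Reconcile the synopsis, protocol 1.4, 3, 7.1.5, 8.3.3, 11.1 and 11.8, and SAP 3 and 4.1, so that they give one time of disclosure to participants and site staff, separate from unblinding of the analysis team.
2. State in 7.1.5, 8.3.3 and SAP 4.1 that a code goes to the participant and to AE-assessing site staff only after that participant's Visit 4 laboratory results and dose-2 diary have been reviewed, and CS/NCS, grade and causality of all AEs through Visit 4 are entered and signed. Add the diary review to 7.1.5. The emergency unblinding provision is not affected.
3. If lock-first release is intended, also amend the Week 12 cross-over in 11.1 and the 60-week total in the synopsis (at least R + 60 weeks).
4. SAP 4.1 is in the past tense, so codes may already be out. Record in the report when they were released relative to these judgements; where release came first, label the Visit 4 CS/NCS and causality assessments as unblinded.

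The cost of steps 1 and 2 is wording plus a delay of roughly the laboratory turnaround for each participant, which the documents do not give. Step 3 costs more: the earliest placebo participants wait until the last Visit 4 and the lock.
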